### 13.6.2 Local investigations whilst on study

These assessments should be conducted in line with standard of care every 3 months during routine follow up visits, and data collected for the trial 6 monthly.

- Physical examination, including clinical assessment of disease and B-CLL in accordance with 2018 iwCLL criteria

- Local haematology and biochemistry test including:
    - FBC (Hb, platelets, WBC count, ANC neutrophils, ALC lymphocytes, reticulocyte count)
    - U&E's (calcium (adjusted), urea, urate, serum creatinine, calculated creatinine clearance)
    - bilirubin, alkaline phosphatase, ALT or AST
  - Blood pressure (monitor participants as appropriate to ensure blood pressure is below 140/90mmHg. Participants with hypertension (either prior to the trial or emergent on treatment) should be managed according to NICE Guidelines (NG136; published August 2019)\*, see Appendix 5, to keep the blood pressure below 140/90mmHg.
- \*with the exception of the excluded concomitant medications listed in section 12.3.2

### 13.7 Randomisation Pathway: Eligibility and Baseline Assessments

For participants entering the Randomisation Pathway, initial assessments aiming to confirm eligibility and provide a baseline for the day-to-day clinical care of participants should be performed within 4 weeks prior to randomisation, unless otherwise stated below. If randomisation does not occur within 4 weeks of confirming eligibility then the tests will have to be repeated. It is expected that all assessments will be performed as part of standard clinical care.

*Potential participants must attend for a face-to-face clinic appointment in order for a medically qualified doctor to assess eligibility for STATIC (even whilst policies are in place to minimise hospital visits during the COVID-19 pandemic or similar epidemic/ pandemic).*

**Any assessments performed specifically for the purposes of the trial must only be performed after full written informed consent has been obtained and the participant has been registered into the trial.**

Cardiac monitoring should be conducted, in line with standard of care. If abnormal cardiac function is identified during screening, and, in the opinion of the PI, meets the following exclusion criterion, then the participant should be excluded from the trial:

*Symptomatic cardiac failure not controlled by therapy, or unstable angina not adequately controlled by current therapy (in patients with a significant cardiac history the left ventricular function should be assessed and patients with severe impairment should be excluded)*

#### 13.7.1 Baseline Local Investigations

Mandatory Investigation to Confirm Eligibility?	Type of Investigation	Comments
Yes	Complete Medical History	Including detailed history of CLL (including duration of treatment with ibrutinib or other BTK inhibitor (date of commencement of ibrutinib, dose, any significant periods of treatment since starting, prolonged (of a month or more) planned and unplanned periods of treatment breaks, history of

		
treatment and how long the potential participant has been in clinical remission (minimum of preceding 12 months), other ongoing medical conditions that require treatment, concomitant medications, IGVH mutation status (if known), and details of any previous COVID-19 vaccinations
 
Within 4 weeks prior to being randomised

Yes	Pregnancy test	Serum or urine HCG in women of child bearing potential within 2 weeks prior to being randomised
Yes	Complete Physical Examination, Vital Signs and Clinical Assessment of Disease	
Within 2 weeks prior to randomisation
 
To confirm potential participant remains in clinical remission:
 
 
- No palpable lymph nodes ;
 
- no palpable spleen;
 
 
- B-CLL in accordance with 2018 iwCLL criteria
 
In addition: pulse rate, height, weight

Yes	Local Haematology and Biochemistry	
To confirm potential participant remains in clinical remission:
 
 
- ALC lymphocyte count below <math>5 \times 10^9/L</math>
 
 
Within 4 weeks prior to being randomised

Yes	WHO performance status	
Within 4 weeks prior to being randomised
 
Refer to Appendix 2.

No	Local Haematology and Biochemistry	
FBC (Hb, platelets, WBC count, ANC neutrophils, ALC lymphocytes, reticulocyte count)
 
Within 2 weeks prior to being randomised

Yes (for previously treated participants only)	Local Haematology and Biochemistry	
U&E's -calculated creatinine clearance
 
Within 4 weeks prior to being randomised

No	Local Haematology and Biochemistry	
U&E's- calcium (adjusted), urea, urate, serum creatinine
 
All tests within 2 weeks prior to being randomised

Yes	Local Haematology and Biochemistry	
LFT's (bilirubin, alkaline phosphatase, ALT or AST)
 
Within 4 weeks prior to being randomised

Yes	Hepatitis B and C	Serology for Hepatitis B and C (HBsAg, HBcAb & HCAb)  (Within 12 weeks prior to randomisation)
Yes	Cardiac Assessment (conducted as per SoC)	Cardiac assessments should be performed as per SoC (if formal assessments, such as an ECHO, are conducted within any time frame the results will be acceptable)
No	Blood pressure	Take/ document blood pressure and monitor participants as appropriate to ensure blood pressure is below 140/90mmHg. Participants with hypertension (either prior to the trial or emergent on treatment) should be managed according to NICE Guidelines (NG136; published August 2019)*, see Appendix 5, to keep the blood pressure below 140/90mmHg. Blood pressure should be reported on the relevant eCRF according to the (CTCAE) V5.0 grades, see Appendix 3.  *with the exception of the excluded concomitant medications listed in section 12.3.2

### 13.7.2 Baseline Central Investigations

The following samples are required from both randomisation arms (pausing ibrutinib and continuous ibrutinib arm) at baseline (these must be collected following registration, prior to randomisation):

- 20ml blood in EDTA to HMDS central laboratory for MRD flow cytometry, B-cell sorting, molecular BTK mutation analysis and for DNA/RNA storage
- 50ml anti-coagulated blood sent to UK CLL Biobank central laboratory
- Saliva Sample sent to the UK CLL Biobank central laboratory

### 13.7.3 Baseline QoL and Health Economic questionnaires

The following questionnaires should be completed in clinic after registration, before treatment is started:

- QoL Questionnaires (EORTC QLQ-C30, QLQ-CLL and EQ-5D-5L)
- Healthcare resource use questionnaire

### 13.8 Randomisation Pathway: Assessments while on study

Participants randomised to the continuous treatment pathway will receive ibrutinib (oral) 420mg per day (or other reduced dose, if that dose has been stable for the past 6 months and there are no unresolved toxicities other stable reduced dose) until active disease leads to the requirement to change to an alternative therapy in the opinion of the local Investigator (strategy failure) or death.

Participants randomised to the intermittent treatment strategy will pause treatment immediately following randomisation, and restart when the restart criteria are met. When treatment restarts, participants restart treatment with ibrutinib at the standard dose (or other reduced dose, if that dose has been stable for the past 6 months and there are no unresolved toxicities) until the treatment stop criteria are met.

The pausing and resuming criteria will be assessed locally every 3 months, at standard clinic visits. Participants can pause and restart treatment multiple times until active disease whilst on treatment leads to the requirement to change to an alternative therapy, death, or the end of the trial. Participants who demonstrate active disease whilst on the treatment pause will initially resume ibrutinib treatment, and the criteria for treatment failure will only be met if active disease is present at the subsequent follow up.

Refer to Section 13.8.3 for pausing and re-starting criteria.

Participants randomised to either pathway will be assessed as per standard of care clinic visits every 3 months, and data collected for the trial 6 monthly.

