### **Randomisation Pathway: overview of pausing / resuming and continuous treatment strategies**

To be eligible for randomisation, previously treated participants will have been treated with continuous ibrutinib for at least 3 years and must have been in clinical remission for at least the last 12 months; whereas front-line participants from FLAIR will have been treated for 6 years with ibrutinib in FLAIR and be in clinical remission for at least the last 12 months. Participants will be randomised 1:1 to either intermittent ibrutinib, known as the 'pausing ibrutinib' arm, or continuous ibrutinib treatment.

*'Continuous ibrutinib' arm*

Participants randomised to continuous treatment will receive ibrutinib (oral) 420mg per day (or other reduced dose, if that dose has been stable for the past 6 months and there are no unresolved toxicities) until strategy failure, defined as active disease as per 2018 iwCLL criteria, death, or the end of the trial.

*'Pausing ibrutinib' arm*

Participants randomised to the 'pausing ibrutinib' arm (intermittent treatment strategy) will pause ibrutinib treatment immediately following randomisation, and restart when the restart criteria are met. When treatment restarts, participants restart ibrutinib treatment at the standard dose (or their previous stable reduced dose) until the treatment pausing criteria are met. The pausing and resuming criteria are assessed locally every 3 months at standard clinic visits. Participants can pause and restart treatment multiple times until treatment strategy failure (defined as active disease per 2018 iwCLL criteria) whilst on treatment, death, or end of the study.

In order to begin the initial ibrutinib pause in the pausing ibrutinib arm, all criteria below must be met and maintained continuously for preceding 12 months:

- No palpable lymph nodes and
- No palpable spleen, and
- ALC  $<5 \times 10^9/L$

Criteria to resume/ restart ibrutinib in 'pausing ibrutinib' arm:

Any one of:

[figure not shown]
- Palpable lymph nodes ( $\geq 2\text{cm}$ ), or
- palpable spleen, or
- ALC  $\geq 5 \times 10^9/L$ .

Criteria for subsequent ibrutinib pause(s) (second and subsequent pausing treatment breaks):

- Received at least a further 12 months of ibrutinib, and
- No palpable lymph nodes, and
- No palpable spleen, and
- $<5 \times 10^9/L$  ALC for at least 6 months.

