### 7.2 Primary objectives

The primary objective is to assess non-inferiority (NI) of the intermittent treatment strategy in terms of time to treatment strategy failure, defined as the first documented instance of active disease (as defined by the 2018 iwCLL criteria) that does not respond to treatment, or death.

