Participants randomised to the intermittent treatment arm will pause ibrutinib treatment immediately following randomisation, and restart when the restart criteria are met (see Section 13.8.3; the restart criteria do not indicate active disease as per 2018 iwCLL criteria). When the re-start criteria are met participants will receive ibrutinib (oral) 420mg per day (or other reduced dose, if that dose has been stable for the past 6 months and there are no unresolved toxicities) until treatment failure (active disease per 2018 iwCLL criteria) whilst on treatment or death. If these participants demonstrate active disease whilst on the planned treatment pause they will initially resume ibrutinib and the criteria for treatment failure would be met if they present with active disease at the next follow up (in which case the time to treatment failure would be backdated to when active disease was first demonstrated). Those randomised to the continuous treatment arm will receive ibrutinib (oral) 420mg per day (or other reduced dose, if that dose has been stable for the past 6 months and there are no unresolved toxicities) until treatment failure (active disease) as per 2018 iwCLL criteria or death.

The Clinical Need pathway is a prospective, national, multicentre, open-label, single-arm, non-randomised cohort to assess the safety and overall survival of patients receiving continuous ibrutinib treatment. Participants exiting the FLAIR trial who are not eligible for randomised study because they have signs of progressive or returning CLL after completing 6 years of ibrutinib treatment within FLAIR, but prior to entry into STATIC, can join the Clinical Need Cohort. Participants in the Clinical Need Cohort

will receive treatment during the trials 6 year recruitment period and for the 3 years of follow up, meaning that participants will be on the trial for between 3-9 years, depending upon when they enter the trial. Up to 30 patients are expected to enter into the Clinical Need Cohort. Patients will continue receiving continuous ibrutinib, either at the standard dose, or a stable reduced dose.

Front-line participants entering either the Randomisation pathway or the Clinical Need cohort from the FLAIR trial should enter STATIC on completion of treatment in FLAIR, with no break in therapy, with the exception of participants who have completed the 6 years of treatment in FLAIR prior to STATIC opening.

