## **12.5 Treatment post-relapse/treatment failure**

Participants randomised to the pausing ibrutinib arm who demonstrate active disease will initially resume ibrutinib treatment. Participants who present with non-responsiveness to the reintroduction of ibrutinib as evidenced by continued active disease as per the 2018 iwCLL criteria, will meet the criteria of treatment failure and this should prompt the discontinuation of ibrutinib and consideration of subsequent therapy off-study at the discretion of the local investigator.

Participants randomised to the continuous ibrutinib arm who demonstrate active disease (see Appendix 1) at any time during the trial will meet the criteria of treatment failure and should be treated off-study at the discretion of the treating clinician.

Participants in the Clinical Need Cohort should continue to receive ibrutinib at the treating clinician's discretion until this is no longer providing benefit. Non-responsiveness to continued ibrutinib, as evidenced by symptomatic active disease, should prompt the discontinuation of ibrutinib and the participant should be treated off-study at the discretion of the treating clinician.

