### **13.10 Active Disease**

#### **13.10.1 Definition of Active Disease**

Participants will be evaluated for progression until the criteria of active disease is met, leading to the requirement to change to an alternative therapy (treatment failure). For participants randomised to the intermittent treatment arm the criteria of active disease must be met whilst the participant is on treatment.

Active disease, defined by the 2018 iwCLL criteria, is characterised by at least one of the following:

- Evidence of progressive marrow failure as manifested by the development of, or worsening of, anaemia and/or thrombocytopenia. Cut-off levels of Hb <10 g/dL or platelet counts <100 × 10^9/L are generally regarded as indication for treatment. However, in some patients, platelet counts <100 × 10^9/L may remain stable over a long period; this situation does not automatically require therapeutic intervention.
- Massive (i.e., ≥6 cm below the left costal margin) or progressive or symptomatic splenomegaly.
- Massive nodes (i.e., ≥10 cm in longest diameter) or progressive or symptomatic lymphadenopathy.
- Progressive lymphocytosis with an increase of ≥50% over a 2-month period, or lymphocyte doubling time (LDT) <6 months. LDT can be obtained by linear regression extrapolation of absolute lymphocyte counts obtained at intervals of 2 weeks over an observation period of 2 to 3 months; patients with initial blood lymphocyte counts <30 × 10^9/L may require a longer observation period to determine the LDT. Factors contributing to lymphocytosis other than CLL (e.g., infections, steroid administration) should be excluded.
- Autoimmune complications including anaemia or thrombocytopenia poorly responsive to corticosteroids.
- Symptomatic or functional extranodal involvement (e.g., skin, kidney, lung, spine).
- Disease-related symptoms as defined by any of the following:
  - a. Unintentional weight loss ≥10% within the previous 6 months.
  - b. Significant fatigue (i.e., ECOG performance scale 2 or worse; cannot work or unable to perform usual activities).
  - c. Fevers ≥100.5°F or 38.0°C for 2 or more weeks without evidence of infection.
  - d. Night sweats for ≥1 month without evidence of infection.

Hypogammaglobulinemia, or monoclonal or oligoclonal paraproteinemia does not by itself constitute a basis for initiating therapy. However, it is recommended to assess the change in these protein abnormalities, if patients are treated.

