## 17.4 Derivation of Endpoints

### 17.4.1 Time to Treatment Strategy Failure

Time to treatment strategy failure is defined as the time from randomisation to time of treatment strategy failure. Treatment strategy failure is defined as the first documented instance of active disease that does not respond to treatment, or death from any cause. If a participant reaches active disease whilst on a break and they continue to meet this criteria whilst on subsequent ibrutinib treatment, then the time of the event is when they first met the criteria for active disease. Individuals who are lost to follow-up, withdraw from all follow-up or continuing with their treatment strategy at the time of analysis will be censored at the date of last assessment. Participants who transfer to an alternate BTK inhibitor without experiencing active disease will be censored at their last assessment pre-transfer.

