### 5.3. Progressive disease

Progressive disease (PD) during or after therapy is characterized by at least 1 of the following, when compared with nadir values (Table 4):

5.3.1. Lymphadenopathy. Progression of lymphadenopathy is often discovered by physical examination and should be recorded at regular intervals. In CLL, the use of imaging (CT scans) usually does not add much information for the detection of progression or relapse. Disease progression occurs if 1 of the following events is observed.

- Appearance of any new lesion such as enlarged lymph nodes ( $\geq 1.5$  cm), splenomegaly, hepatomegaly, or other organ infiltrates. Transient increases of lymph node size during treatment with novel inhibitors may occur and should not be counted as PD.
- An increase by  $\geq 50\%$  in greatest determined diameter of any previous site ( $\geq 1.5$  cm).

5.3.2. An increase in the spleen size by  $\geq 50\%$  or the de novo appearance of splenomegaly. In the setting of splenomegaly, the splenic length must increase by  $\geq 50\%$  of the extent of its prior increase beyond baseline (eg, a 15-cm spleen must increase to  $\geq 16$  cm). If no prior splenomegaly was observed at baseline or if splenomegaly has resolved with treatment, the spleen must increase by at least 2 cm from baseline.

5.3.3. An increase in the liver size of  $\geq 50\%$  of the extent enlargement of the liver below the costal margin defined by palpation, or the de novo appearance of hepatomegaly. Given the impact of numerous medical conditions, liver size by physical examination or by CT scan is not a reliable measure of hepatic involvement by CLL and should only be counted if hepatomegaly is clearly attributable to lymphoid involvement.

5.3.4. An increase in the number of blood lymphocytes by 50% or more with at least  $5 \times 10^9/L$  B lymphocytes. Certain therapies (eg, kinase inhibitors) may cause lymphocytosis. In the setting of therapy with such agents, an increase in blood lymphocyte count by itself does not uniformly indicate an increased tumour burden, but may reflect redistribution of leukaemia cells from lymphoid tissues to the blood. This should be predefined in the protocol of clinical trials for therapies in which redistribution of disease occurs. In such cases, increased lymphocytosis alone is not a sign of treatment failure or PD.

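### The primary event, treatment strategy failure, is worded in conflicting ways, and the rule on kinase-inhibitor lymphocytosis is not carried into its definition

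*Protocol*

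**What the plan says.** The protocol describes the event in these ways.

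- **Non-response wording.** Section 7.2: "defined as the first documented instance of active disease (as defined by the 2018 iwCLL criteria) that does not respond to treatment, or death". Section 17.4.1: "Treatment strategy failure is defined as the first documented instance of active disease that does not respond to treatment, or death from any cause". Section 8.1 opens with the same idea.
- **Active disease alone, continuous arm.** Section 3 has patients treated "until strategy failure, defined as active disease as per 2018 iwCLL criteria, death, or the end of the trial". Section 12.5 speaks of continuous-arm participants "who demonstrate active disease (see Appendix 1) at any time during the trial will meet the criteria of treatment failure". The continuous-arm text in 8.1 agrees with these two.
- **Active disease plus a need to change therapy.** Section 13.8, continuous arm: "until active disease leads to the requirement to change to an alternative therapy in the opinion of the local Investigator (strategy failure) or death". Section 13.10.1 also ties failure to a requirement to change therapy, without naming whose opinion decides.
- **Pausing arm, active disease during a pause.** Section 8.1: "the criteria for treatment failure would be met if they present with active disease at the next follow up", with the event backdated to the first active disease. Sections 12.5, 13.8 and 17.4.1 use the same persistence test, and 17.4.1 also backdates.

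Active disease needs only one listed criterion. One of these is a lymphocyte rise of at least 50% over 2 months or a doubling time under 6 months. The only exclusion attached to it is for causes other than CLL. Appendix 1, section 5.3.4, under progressive disease, deals with kinase-inhibitor lymphocytosis: "In such cases, increased lymphocytosis alone is not a sign of treatment failure or PD". It adds that trial protocols should predefine this. Sections 13.10.1 and 17.4.1 do not.

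**The concern.** Sites recognise and report failure from Sections 12 and 13; the endpoint is derived from Section 17. If the wordings are not equivalent, the primary event depends on which section was followed. The need-to-change-therapy wording makes the event depend partly on a clinician's decision. The trial is open-label and disease is assessed locally, so that decision can differ between arms for the same clinical state.

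The lymphocyte criterion adds a second route to misclassification. Redistributed cells after restarting ibrutinib are CLL cells, so an exclusion for non-CLL causes does not reach them. Restarting is built into the pausing strategy, and visits are every 3 months. A rise seen soon after restart could therefore be recorded as active disease on treatment.

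**Working it through.** **Step 1: apply each wording to the same patient.**

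| Patient | Sections 3, 8.1, 12.5 | Sections 13.8, 13.10.1 | Sections 7.2, 17.4.1 |
|---|---|---|---|
| A. Continuous arm, active disease on ibrutinib, kept on ibrutinib | Event | Not an event until a change of therapy is required | Depends on what non-response means for someone already on the drug; not stated |
| B. Pausing arm, restarted without active disease, then an isolated lymphocyte rise of at least 50% over 2 months, kept on ibrutinib | Event under 3 and 8.1 (active disease on treatment) if the active-disease list is read alone; not an event if Appendix 1, 5.3.4 is applied | Not an event, since therapy is unchanged | Not stated |
| C. Pausing arm, active disease on a pause, restarted, still active at next follow-up | Event (8.1, 12.5); 8.1 backdates | Event under the persistence test in 13.8 | Event under 17.4.1, backdated |

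A and B change status with the section used. Sections 8.1, 12.5, 13.8 and 17.4.1 agree on C.

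**Step 2: reproduce the plan's event number.** Inputs from Sections 18.1 and 8.1: one-sided alpha 2.5%, power 80%, margin 1.33, 1:1 allocation, 379 events. With a true HR of 1, events = 4 × (1.960 + 0.842)² / (ln margin)².

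- Margin 1.33: 386.0, rounded up to 387.
- Margin 4/3: 379.4, rounded up to 380.

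The stated 379 is reproduced to within 3% either way. Power with 379 events at margin 1.33 is Φ(√379/2 × ln 1.33 − 1.96) = 79.3%. At the 2.35% level that Section 19.3.1 sets for the final test it is 78.5%. The largest HR that still passes is 1.33 × exp(−1.96 × 2/√379) = 1.087; Section 18.1 prints 1.08.

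**Step 3: sensitivity to spurious pausing-arm events.** The documents give no rate of restart lymphocytosis, so the count k is an assumption shown as a range. Hold the total at 379 and let the true HR be 1. Genuine events per arm are e = (379 − k)/2, the observed HR is approximately (e + k)/e, and power is Φ(√379/2 × ln(1.33/HR) − 1.96).

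| k | e | HR | Power |
|---|---|---|---|
| 0 | 189.5 | 1.00 | 79% |
| 5 | 187 | 1.03 | 71% |
| 10 | 184.5 | 1.05 | 62% |
| 20 | 179.5 | 1.11 | 42% |

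Here k counts net extra events. Some misclassified patients would have failed later anyway. At the planned overall proportion, 379/800 = 47%, k net events correspond to roughly k/0.53 misclassified patients: about 9 for k = 5 and 38 for k = 20. This ignores lost follow-up time, which partly offsets it.

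**The case against.** A fair defence has several parts.

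- **Non-response.** Active disease while taking ibrutinib is arguably already non-response, so 17.4.1 and 12.5 may mean the same thing in the continuous arm. That is reasonable, but it leaves the extra condition in 13.8 and 13.10.1 unexplained.
- **Lymphocytosis.** The protocol is not silent. Section 16 refers active disease and response to Appendix 1, and 5.3.4 names treatment failure as well as progressive disease. The list also warns that counts below 30 × 10⁹/L may need longer observation to establish the doubling time. Under 13.8 and 13.10.1 a transient rise without a change of therapy would not count. All of this stands. The defect is that the rule sits under progressive disease, is not carried into the event definition, and protects patient B under some sections only.
- **Direction.** Spurious pausing-arm failures cost power; they do not manufacture non-inferiority. This also stands. The effect of the investigator-opinion wording has no known direction or size.

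A reader might infer three stronger points, which the documents do not support.

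- *Only the pausing arm can have restart lymphocytosis.* Continuous-arm patients can restart after surgical interruptions (12.3.5) or toxicity breaks (17.4.6). FLAIR completers exempt from the no-break rule (8.1) may restart at entry.
- *Section 13.10.1 contradicts the backdating in 17.4.1.* Section 13.10.1 says: "For participants randomised to the intermittent treatment arm the criteria of active disease must be met whilst the participant is on treatment". Section 17.4.1 also requires active disease to persist on resumed ibrutinib, and backdating only sets the date.
- *Stable disease after restart counts as failure.* That sets generic iwCLL text in Appendix 1 (5.4 and 5.5) against the protocol's own test in 12.5, which is continued active disease.

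**Conclusion.** The primary event is inconsistently defined, and this can change whether a given patient counts. The main conflict is between Sections 3, 8.1 and 12.5, which count any active disease in the continuous arm, and Sections 13.8 and 13.10.1, which add a need to change therapy. The lymphocytosis rule is a related gap: it is present in Appendix 1 but not predefined where the event is defined.

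The ascertainment risk from the investigator-opinion wording is real but cannot be quantified from the documents. For lymphocytosis, the figures rest on assumed counts of 5 to 20 net spurious events, all in the pausing arm, with a true HR of 1. On that basis the HR moves to about 1.03 to 1.11 and power falls to between 71% and 42%. About 15 to 20 such events are enough to reach or exceed the largest estimate that can pass. The stated 379 events are not called into question.

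**What to change.** In Section 17.4.1, state one endpoint-counting rule for both arms that does not depend on the investigator's decision to change therapy. Keep the existing rule for active disease on a pause: confirmed at the next follow-up after restart and dated to first occurrence. Cross-refer to 17.4.1 from Sections 3, 8.1, 12.5, 13.8 and 13.10.1 in place of restating the event.

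In the same place, state for endpoint counting how Appendix 1, 5.3.4 applies to the lymphocyte criterion. Isolated redistribution lymphocytosis after a restart, in either arm, should not count; sustained progression should. The wording needs a way to tell these apart, otherwise a lasting isolated rise would never become an event.

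The treatment-stopping wording in 12.5 and 13.8 also conflicts and must be reconciled by the clinical team. The endpoint rule need not settle it.

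The cost is a protocol amendment and matching guidance for the Active Disease eCRF. No extra visits are needed.
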